## **Study Population**

Subjects will be healthy females, ages 18 to 65 years. Up to 50 subjects will be screened in order to enroll up to 25 subjects.

Results from this protocol will be used to support future research with breast cancer patients; therefore, only women will be enrolled in the study. The protocol was approved by NIH review panel and program officer to study only female participants.

We plan to enroll 5 subjects to each of the 5 cohorts for a total of up to 25 subjects.

Participants will be recruited using the UAMS Translational Research Institute (TRI) Research Participant Registry, ARresearch.org. After the list of potential participants is obtained from TRI, we will contact the individuals via email, if indicated as their communication preference. The email we will use when communicating with potential participants is included in the IRB submission.

Participants will also be recruited using the Facebook pages of UAMS, TRI, and the Winthrop P. Rockefeller Cancer Institute. Participants may also be recruited at Community or University events, or from within UAMS via word of mouth.

Subjects will be asked to self-report on the inclusion/exclusion criteria. However, a baseline blood sample will be obtained to rule out anemia and pregnancy and to determine liver and kidney function.

#### Inclusion Criteria

- Female
- Age 18-65 years

#### Exclusion Criteria

- Women who are pregnant or breastfeeding
- Presenting with an acute illness (may re-screen again in two weeks if illness has subsided)
- Anemia (Hb < 12 g/dL for females)
- Calculated Creatinine Clearance less than 60 mL/min
- Liver function tests outside of normal range
- Unwilling to refrain from alcohol consumption for 48 hours

Participants with medical information suggestive of a chronic medical condition may be excluded from the research at the enrolling physician's discretion.

Repeat screening blood tests may be done at the discretion of the enrolling physician and/or principal investigator. All screening tests will be paid for by the research grant.

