## Study Design and Procedures

This is a Phase 1 trial to determine time course and dose of dexrazoxane pre-treatment for optimal degradation of Topoisomerase 2 b (Top2b) in human volunteers. The FDA recommended dose of Dexrazoxane is 10 times the dose of Doxorubicin. All the doses in this protocol are in the FDA approved range and have been prescribed for many years.

There will be 5 cohorts for different doses: 100mg/m^2, 200 mg/m^2, 300 mg/m^2, 400 mg/m^2, or 500 mg/m^2. Our plan is to enroll up to 5 subjects per cohort. We will start with 100 mg/m^2 and analyze the Top2 protein level from up to five subjects. Doses will escalate to

200 mg/m^2, 300 mg/m^2, 400 mg/m^2, and 500 mg/m^2. If 100 mg/m^2 dexrazoxane is insufficient, we will increase the dose to find the optimal dose.

A blood sample will be obtained at screening to rule out anemia, pregnancy and to determine liver and kidney functions. If the serum pregnancy test is not performed at the time of the initial screening blood draw and another attempt is required in order to perform this test, a urine pregnancy test can be used as a substitute. A urine pregnancy test will be done on the day of the 12-hour infusion visit, prior to infusion.

Subjects will be administered a dose of dexrazoxane by IV infusion over 15 (+/- 5) minutes.

Blood will be drawn to purify peripheral blood leukocytes for Top2b and Top2a assessment using Western blot analysis. 20 mL of blood will be drawn before dexrazoxane infusion. 10 mL of blood will be drawn hourly (+/- 5 minutes) after the start of infusion for 12 hours. The final lab draw of the 12-hour infusion day may occur at 6:30 pm based on facility and staff availability. The final blood draws occur at 24 hours (+/- 2 hours); and 48 hours (+/- 2 hours) from the start of infusion. A total of 17 blood samples will be drawn for each subject.

Subjects will be screened for COVID at each visit per institutional standards. Subjects who do not pass the screening will not be permitted to continue with the study.

Vital signs will be recorded at the following time points: 1) screening, 2) pre-infusion, 3) end of infusion, 4) 6 hours post-infusion, 5) 12-hours post infusion/discharge. Vital signs to be captured include: heartrate; respirations; blood pressure; temperature; pain (rate pain on scale of 1-10). Height and Weight will also be recorded at screening.

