A parking voucher will be provided for each visit. During the first 12 hours after infusion, meals and a parking voucher will be provided.

Each subject will have a safety CBC one week (+/- 2 days) after dexrazoxane infusion to rule out myelosuppression. If the one-week post-study blood counts are below normal range, subject will have additional CBC two weeks post-infusion.

Treatment failure and subject removal criteria includes: subject noncompliance with blood draw, or, subject develops rare hypersensitivity reactions to dexrazoxane infusion.

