#### **Risks and Benefits**

Some subjects may experience discomforts, or pain on intravenous injection of dexrazoxane. We will minimize this risk by administering dexrazoxane as an IV infusion

over 15 (+/-5) minutes. If a participant reports pain during the infusion, the catheter will be checked to ensure it is properly inserted. If no problems are noted with the catheter, the rate of the infusion will be slowed. There is a very low probability that a subject may develop subcutaneous and cutaneous necrosis. Subjects will be informed and instructed to report to study team if she develops this side effect. PI and study team members will arrange for medical care and expect full recovery on this.

To reduce the risk of bruising and pain from multiple injections, the twelve hourly blood draws will be drawn from the IV catheter. If the initial IV line stops working for any reason, a new line will have to be placed.

There is a very low probability that a subject may develop myelosuppression. Each subject will have screening CBC one week after dextrazoxane infusion to rule out myelosuppression. The study team will arrange for medical care and expect recovery if a subject develops myelosuppression. If the one-week post-study blood counts are not within normal range, subject will have additional CBC at 2 weeks post-infusion.

The risk of allergic reaction is very low. In a rare situation, if the participant develops allergic reaction to dextrazoxane, the infusion will be stopped.

Other adverse events may include:

- Bluish color
- changes in skin color
- chest pain or tightness in the chest
- chills
- cold hands and feet
- cough, sneezing, sore throat
- difficult or labored breathing
- fever
- hoarseness
- lower back or side pain
- pain, redness, or swelling in the arm or leg
- painful or difficult urination
- swelling of the hands, ankles, feet, or lower legs
- tenderness
- unusual bleeding or bruising
- unusual tiredness or weakness)

All unanticipated problems or deviations should be reported immediately to principal investigator/sponsor. The immediate reports should be followed promptly by details written reports to investigator/sponsor. All reports will identify subjects by unique code numbers assigned rather than other identifiers. Unanticipated problems will be reported to IRB within 5 days of becoming aware of an event.

A risk to study participants is the potential for loss of confidentiality of study data.

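### Hemoglobin is the only blood count with an exclusion limit and no pre-dose CBC is required, although myelosuppression is a named risk checked by CBC one week after infusion

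*Protocol*

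**What the plan says.** The protocol describes the pre-dose blood test twice, by purpose and not by panel. Study Design and Procedures has "A blood sample will be obtained at screening to rule out anemia, pregnancy and to determine liver and kidney functions". Study Population says that "a baseline blood sample will be obtained to rule out anemia and pregnancy and to determine liver and kidney function", directly after stating "Subjects will be asked to self-report on the inclusion/exclusion criteria".

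The Exclusion Criteria contain three laboratory limits. One is a blood count, "Anemia (Hb < 12 g/dL for females"; the others concern creatinine clearance and liver function tests. There is no limit for leukocytes, neutrophils or platelets.

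On the marrow, Risks and Benefits states "There is a very low probability that a subject may develop myelosuppression" and continues "Each subject will have screening CBC one week after dextrazoxane infusion to rule out myelosuppression". Study Design and Procedures orders the same one-week test, with a window of two days either side, and adds "If the one-week post-study blood counts are below normal range, subject will have additional CBC two weeks post-infusion".

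**The concern.** The protocol treats three organ systems differently before dosing. Liver and kidney each have an explicit entry limit. The marrow, which the protocol itself names as a possible site of toxicity, is covered by hemoglobin alone. The cell lines that a myelosuppression check also looks at (leukocytes, neutrophils, platelets) have no entry limit and no required baseline.

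Two things are at stake. The first is safety: Risks and Benefits says that participants have no direct benefit, so a woman with a silent low count should not be dosed without anyone knowing. The second is attribution. The one-week CBC is judged against the normal range, not against the woman's own earlier value. If it is low, someone must decide whether it is an adverse event, to be classified under CTCAE and sent to the safety officer, or a state that was there before. The protocol requires no value that would settle this. With up to five women per dose cohort, one wrongly attributed low count is 1/5 = 20% of a full cohort's blood-count safety record.

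**Working it through.** This is mainly a question of what is written, so the relevant places are set side by side.

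**Tests and limits**

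| Item | Before dosing | After dosing |
|---|---|---|
| Hemoglobin | Measured to rule out anemia; exclusion below 12 g/dL | Part of the one-week CBC |
| Leukocytes, neutrophils, platelets | Not named; no limit | CBC at one week; repeat at two weeks if low |
| Liver, kidney | Measured; exclusion limits given | None ordered |

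In the protocol the term CBC is attached only to tests after the infusion. The 20 mL pre-infusion draw stands in the paragraph on the Western blot, and no count is ordered from it.

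**Can another rule exclude a woman with a low count?** Self-report cannot detect a count that causes no symptoms. The physician may exclude for a suggested chronic condition, but this is optional and needs a measured count to act on. The acute-illness exclusion catches some illness-related low counts, but only in women who present as ill. None of these is a count limit, so a woman with a silent low neutrophil or platelet count passes the list when it is followed exactly.

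**Does the fix need another blood draw?** The protocol states "A total of 17 blood samples will be drawn for each subject". That total is reproduced by: screening 1 + pre-infusion 1 + hourly 12 + 24 h 1 + 48 h 1 + one week 1 = 17. Two of the 17 precede dosing, so a CBC can be run on blood already being taken.

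**Room for screen failures.** Up to 50 screened − up to 25 enrolled = 25 from all causes.

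**Added screen failures.** The documents give no share p of otherwise eligible women with at least one low count, so this is an assumption. If each normal range is a central 95% interval, 2.5% lie below it for each of the three counts. That gives p = 2.5% if the three overlap fully and 3 × 2.5% = 7.5% if they do not overlap; 1% allows for a healthier group. Expected added failures are 50p:

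- p = 1%: 0.5
- p = 2.5%: 1.25
- p = 7.5%: 3.75

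At the top of the range this takes 3.75/25 = 15% of the available room.

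**The case against.** The strongest reply is that the protocol lists purposes and names no panel at all. Hemoglobin comes from a hematology test, and nothing says that it is measured alone. A reader might infer from the text that no full count is taken before dosing. The documents do not support that: they neither require one nor rule one out. If a full count is run in practice, a baseline exists and the attribution problem largely goes away. The missing entry limit remains either way, because nothing tells staff what to do with a low neutrophil or platelet result.

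The second reply is that the risk is small and watched. The protocol rates it very low, gives one infusion at 500 mg/m² or below, describes all doses as within the approved range, and repeats a low CBC. The investigators and a safety officer monitor closely, and non-serious adverse events also go to the safety officer. This stands and keeps the point modest. But apart from the acute-illness exclusion and the physician's discretion, these checks act after dosing. The two-week repeat helps only partly, since a count that stays low fits either a pre-existing state or slow recovery.

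Two further inferences should be resisted. A reader might want to put a probability on an ambiguous one-week result. The documents give no prevalence, such a figure would apply only if screening yields hemoglobin alone, and counts near the limit can cross it by chance even with a baseline. A reader might also take the word screening, applied in Risks and Benefits to the one-week CBC, as an error. The sentence dates the test after infusion and can be read as screening for the toxicity, so this is editorial at most.

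**Conclusion.** The point holds as a gap in eligibility and baseline testing. The exclusion list, followed exactly, admits a volunteer with an unrecognised low leukocyte, neutrophil or platelet count, and the one-week CBC has no required pre-dose counterpart. The first part rests on the text alone. The second has practical force only if screening does not already yield a full count, which the protocol leaves open.

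The size is modest. It does not touch the choice of dose, which depends on Top2b falling below 5% of baseline. It concerns the protection of women who gain nothing directly, and the ability to read a low safety count. Screening tests and entry limits are protocol content, so the point is not one to leave to a statistical analysis plan. It is worth making because the remedy is cheap, not because the expected harm is large.

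**What to change.** Make three small changes to the protocol.

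1. In Study Design and Procedures and in Study Population, state that a CBC with differential and platelets is run on the existing screening sample.
2. In Exclusion Criteria, add one line: *leukocyte, absolute neutrophil or platelet count below the laboratory's lower limit of normal on the screening CBC (may be repeated)*. This uses the same threshold that already triggers the two-week CBC, so no new number has to be chosen. The protocol already permits repeat screening tests.
3. In Study Design and Procedures, state that the one-week CBC is compared with the screening CBC as well as with the normal range.

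The cost is no added draw and at most one added laboratory test per woman screened (up to 50), or none if a full count is already run. The downside is some exclusions for mildly low and probably harmless counts, about 0.5 to 3.75 of 50 under the assumed 1% to 7.5%. Allowing a repeat test should lower this where the low value was transient.

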#### **Risks and Benefits**

Some subjects may experience discomforts, or pain on intravenous injection of dexrazoxane. We will minimize this risk by administering dexrazoxane as an IV infusion

over 15 (+/-5) minutes. If a participant reports pain during the infusion, the catheter will be checked to ensure it is properly inserted. If no problems are noted with the catheter, the rate of the infusion will be slowed. There is a very low probability that a subject may develop subcutaneous and cutaneous necrosis. Subjects will be informed and instructed to report to study team if she develops this side effect. PI and study team members will arrange for medical care and expect full recovery on this.

To reduce the risk of bruising and pain from multiple injections, the twelve hourly blood draws will be drawn from the IV catheter. If the initial IV line stops working for any reason, a new line will have to be placed.

There is a very low probability that a subject may develop myelosuppression. Each subject will have screening CBC one week after dextrazoxane infusion to rule out myelosuppression. The study team will arrange for medical care and expect recovery if a subject develops myelosuppression. If the one-week post-study blood counts are not within normal range, subject will have additional CBC at 2 weeks post-infusion.

The risk of allergic reaction is very low. In a rare situation, if the participant develops allergic reaction to dextrazoxane, the infusion will be stopped.

Other adverse events may include:

- Bluish color
- changes in skin color
- chest pain or tightness in the chest
- chills
- cold hands and feet
- cough, sneezing, sore throat
- difficult or labored breathing
- fever
- hoarseness
- lower back or side pain
- pain, redness, or swelling in the arm or leg
- painful or difficult urination
- swelling of the hands, ankles, feet, or lower legs
- tenderness
- unusual bleeding or bruising
- unusual tiredness or weakness)

All unanticipated problems or deviations should be reported immediately to principal investigator/sponsor. The immediate reports should be followed promptly by details written reports to investigator/sponsor. All reports will identify subjects by unique code numbers assigned rather than other identifiers. Unanticipated problems will be reported to IRB within 5 days of becoming aware of an event.

A risk to study participants is the potential for loss of confidentiality of study data.

Measures to protect the confidentiality of study data will be implemented as described in the Data and Safety Monitoring Plan section below.

There will be no direct benefits to the study participants; however, knowledge gained from the study could potentially benefit patients in the future.

### **Subject Compensation**

Subjects completing all study visits will receive \$400 compensation for their time. Subjects will be issued a Greenphire, Inc. ClinCard, which is a debit card that the stipends are loaded onto and can be used at their discretion. When a visit is completed, funds will be approved and loaded onto the card. Once approved to be released to the cards, the funds will be available for use.

Subjects who partially complete the study will receive prorated compensation as described below.

Screening - \$50

Infusion – \$80

12-hr blood draws – \$10 per blood draw (maximum of \$120)

24-hr blood draw – \$50

48-hr blood draw – \$50

1-week post infusion lab draw - \$50

A parking voucher will be provided for each visit. Meals vouchers will also be provided to the subjects during the 12 hour infusion visit at visit 2.

### **DATA AND SAFETY MONITORING PLAN**

Overall framework for safety monitoring and what information will be monitored.

**Plan for data management:** A password-protected database will be used to manage all study data. To ensure confidentiality only subject ID numbers will be entered into the database.

Paper records will be stored in the the PHOENIX 1 Clinical Trial office. The records are stored in a double locked file cabinet, in the locked office. Only study staff will have access. Consent and HIPAA will have direct identifiers. Other paper source documents will be coded and the key to the code will be stored separately. Data from the de-identified source documents will also be stored on a password locked Microsoft Excel Spreadsheet located in a secure Box folder. Only study staff will have access to this document. Records may be retained indefinitely, and at minimum, will be retained in accordance with institutional policy and applicable regulatory requirements. A UAMS approved vendor will be used to destroy documents. The key to the code will be destroyed at this time and thereby creating a de-identifiable data with the exception of the consent.

Participants will not be individually identified in any publication. Participants' right to privacy will be protected.

**Plan for safety monitoring:** The data and safety monitoring plan (DSMP) for this trial focuses on close monitoring by the PIs and the safety officer. QA monitoring will also be performed by independent Winthrop P. Rockefeller Cancer Institute staff.

**Frequency of monitoring:** Monitoring will include enrollment, attrition, efficacy endpoints, and adverse events. In addition to monitoring by the PIs, study coordinator, and safety officer monitoring, the University of Arkansas for Medical Sciences IRB monitors all aspects of the project on an annual basis. The frequency of the structured data review for this study can be summarized below.

**Data type Frequency of review**

Subject accrual (adherence to protocol regarding demographics, inclusion/exclusion): At the end of each recruitment

Adverse event rates (injuries): semi-annually

Compliance to treatment: semi-annually

Out of range laboratory data: semi-annually

Stopping rules report regarding statistical power implications of dropouts and missing data: semi- annually

IRB review: annually

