### **Data Analysis**

The goal of this protocol is to find the effective dose of dexrazoxane in degrading Top2b for the subsequent randomized clinical trial. We will select a dose of dexrazoxane, which reduces Top2b to less than 5% of baseline level in 8 hours in 5 volunteers. FDA recommended dose of dexrazoxane is 10 times the dose of doxorubicin. In the attached FDA approval documentation of dexrazoxane, 500mg/m^2 is cited as a recommended dose. We will study dose levels 500mg/m^2 or below. Healthy volunteers will be administered a dose of dexrazoxane. Blood will be drawn to purify peripheral blood leukocytes for Top2b and Top2a assessment using Western blot analysis. The following time points will be assessed: Pre-infusion, 1, 2, 3, 4, 5, 6, 7, 8, 9, 10, 11, 12, 24, and 48 hours after start of dexrazoxane infusion. Each dose level will be administered to up to five subjects, starting with an initial dose of 100 mg/m^2, and escalating in 100 mg increments.

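### Opening the next dose level is tied to the Top2 result but not to the one-week blood counts, and structured safety review is semi-annual rather than per dose level

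*Protocol*

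**What the plan says.** **Escalation.** Study Design and Procedures starts at 100 mg/m² and says the team will "analyze the Top2 protein level from up to five subjects". If that dose of "dexrazoxane is insufficient, we will increase the dose to find the optimal dose". Data Analysis gives the target: "We will select a dose of dexrazoxane, which reduces Top2b to less than 5% of baseline level in 8 hours in 5 volunteers". Both sections describe 100 mg steps up to 500 mg/m², with up to five women per level. Neither mentions blood counts, adverse events or the safety officer's agreement as a condition for the next level.

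**Timing.** The last Top2 draw is at "48 hours (+/- 2 hours) from the start of infusion". The safety CBC, whose stated purpose is to exclude myelosuppression, follows one week after infusion, plus or minus 2 days, and is repeated at two weeks if counts are low.

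**Review schedule.** The list of data types and review frequencies in the Data and Safety Monitoring Plan has "Adverse event rates (injuries): semi-annually" and "Out of range laboratory data: semi-annually". Accrual, in the same list, is reviewed "At the end of each recruitment". The only line there that mentions stopping rules concerns power, dropouts and missing data.

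**Other oversight.** The Data and Safety Monitoring Plan describes close monitoring by the PIs and safety officer. The adverse event section sends serious and non-serious events to the safety officer. Risks and Benefits requires immediate reporting of unanticipated problems.

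**The concern.** Dosing cohorts in sequence protects later volunteers only if the earlier volunteers' safety data are seen before the dose goes up. Here the data that drive escalation are complete by day 2, and the test for the named haematological risk comes later. The scheduled safety reviews follow the calendar, not the dose level. The participants are healthy women who, the protocol says, have no direct benefit to expect. At stake is whether a safety test already planned for every woman informs the decision it could most usefully inform.

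This is a matter of trial conduct, so a separate statistical analysis plan would not normally supply the missing condition.

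**Working it through.** **Inputs from the protocol**
- Five dose levels with up to 5 women each: 5 × 5 = 25, which matches the stated maximum. There are four escalation steps and up to 20 women above the first level.
- Last Top2 draw: 48 h ± 2 h, so about day 2.
- Safety CBC: 7 ± 2 days, so day 5 to day 9.
- Structured review of adverse events and laboratory data: every six months, taken as 182 days.

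**Step 1. Gap for one woman.** CBC day minus last Top2 day: 5 − 2 = 3 to 9 − 2 = 7 days. With the ± 2 h window it is 5 − 50/24 = 2.9 to 9 − 46/24 = 7.1 days. The 8-hour sample, which carries the selection criterion, precedes the CBC by 5 − 8/24 = 4.7 to 9 − 8/24 = 8.7 days. The last draw is used below because it gives the smaller gap.

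**Step 2. Effect of blot turnaround.** Turnaround T is not stated, so a range is assumed. The remaining gap is max(0, gap − T).

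| T (days) | Gap per step (days) | Over four steps (days) |
|---|---|---|
| 0 | 3 to 7 | 12 to 28 |
| 1 | 2 to 6 | 8 to 24 |
| 3 | 0 to 4 | 0 to 16 |
| 5 | 0 to 2 | 0 to 8 |
| 7 or more | 0 | 0 |

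**Step 3. Which women are affected.** Count days from the last woman's infusion. A woman infused d days before her has her CBC on day 5 − d to 9 − d. That falls by day 2 once d is 3 (early CBC) to 7 (late CBC). The gap therefore concerns the last-dosed woman and any others dosed within about 3 to 7 days of her.

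**Step 4. How far escalation can run between structured reviews.** Enrolment pace is not stated. Assume a steady L days per level, with the six-month clock starting at first dosing. Women in completed levels above the first = 5 × min(4, floor(182/L) − 1).

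| L (days) | floor(182/L) | Women above first level |
|---|---|---|
| 36 | 5 | 20 |
| 45 | 4 | 15 |
| 60 | 3 | 10 |
| 90 | 2 | 5 |
| 120 | 1 | 0 |

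All 20 are reached only if 5L ≤ 182, that is L ≤ 36.4 days. Women in a partly filled level are not counted.

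**Step 5. Does another stated rule close the gap?** The removal criteria (noncompliance, hypersensitivity) act on the individual subject. The stopping-rules line is about power. The repeat-CBC rule and adverse event reporting ensure that findings are noticed. None of them makes the next level wait.

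**The case against.** The strongest reply is that the semi-annual lines do not govern when results are read. The two-week repeat works only if someone reads each one-week CBC within days. Adverse events also go to the safety officer, and the list describes structured review only. This stands. A reader might infer that abnormal counts could lie unseen for six months; the repeat-CBC rule rules that out. What it does not do is make escalation wait for the reading.

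Second, the gap does not cover a whole cohort unless the five women are infused almost together, and slow blots remove it. Both points stand and limit the claim.

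Third, a reader might count every level opened within 182 days as fully dosed, giving 20, 15, 10 and 5 women at 45, 60, 90 and 120 days per level. That is too high. At 45 days the fifth level opens on day 4 × 45 = 180, leaving two days to dose five women. The completed-level counts in the working are the supportable ones.

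Fourth, this is a pharmacodynamic search at known doses, not a search for a tolerated dose: "All the doses in this protocol are in the FDA approved range and have been prescribed for many years". The top dose is one the protocol cites as recommended, and Risks and Benefits calls myelosuppression very unlikely. That lowers the severity but does not supply the missing link.

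Finally, a portion of the protocol next to the adverse event section was not available to us, so a hold rule there cannot be excluded.

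**Conclusion.** The point holds in a limited form. In the text available, escalation depends only on Top2, and structured review of adverse events and out-of-range laboratory data is not tied to dose level. With fast blots, a higher dose can be given before the one-week CBCs of the last-dosed women at the current level are known. The window is 3 to 7 days after the last Top2 draw and vanishes at a turnaround of 7 days or more.

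The six-month exposure counts rest wholly on an assumed steady pace, and the conclusion does not depend on them. The documents do not support a claim that safety data go unread, that toxicity is expected, or that the whole cohort's counts would be missing. Severity is low. The change is still worth making, because it uses a test and reviewers already in place.

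**What to change.** 1. In Study Design and Procedures and in Data Analysis, state that the next dose level opens only after the PIs and safety officer have reviewed the one-week CBCs and CTCAE-graded adverse events of all women dosed at the current level.
2. In the review-frequency list, add a review at the end of each dose level to the lines for adverse event rates and out-of-range laboratory data, and keep the semi-annual review.

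Whether to wait for a two-week repeat CBC, or to set a numeric pause threshold, can be left to the PIs and safety officer.

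**Cost.** A short amendment, with no new visit, test or committee. The delay is about 3 to 7 days per step beyond the last Top2 draw (12 to 28 days over four steps), plus CBC turnaround and review time. It shrinks or disappears if blots are slow. If the team had meant to escalate on the 8-hour sample alone, the wait from that sample is 4.7 to 8.7 days. Choosing to wait for a two-week repeat would hold that step until about day 14, which is 14 − 2 = 12 days after the last Top2 draw.
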